**4.1.6.1 Missed Doses of MEDI3506 or Dapagliflozin**

A subject who misses a scheduled dosing visit of MEDI3506 (due to COVID-19 or other reasons) can continue study intervention if dosing is performed within 14 days of the missed visit (Table 4). If subjects cannot be rescheduled within 14 days, the dose is considered missed and study intervention should continue at the next scheduled visit per Table 6. Up to 1 dose of MEDI3506 may be missed. If the subject misses more than one dose, he/she will be considered dropped out/discontinued.

Missed/delayed doses should be captured in the eCRF. Refer to Appendix F for information on dealing with missed doses as a result of the COVID-19 pandemic.

**Table 4 Guidelines for Handling Missed Doses of MEDI3506**

Missed visit	Subject to be rescheduled for dosing within 14 days of missed visit. If subject is unable to be rescheduled within 14 days, skip dose (see below for missed dose).
1 missed dose	Administer next dose according to schedule
2 missed doses	Subject to be considered dropped out/discontinued

Missed doses of dapagliflozin should be handled as detailed in Section 4.7.3.

#### **4.1.7 Replacement of Subjects**

Subjects who are randomized but do not receive investigational product (MEDI3506 or placebo) may be replaced (with identical investigational product assignment, if applicable) to maintain the stipulated cohort sizes. This would include subjects who are randomized and then withdraw consent before receipt of the investigational product.

Subjects who are discontinued from further dosing or follow-up procedures or withdraw their informed consent to all follow-up prior to the end of study (EOS) visit may be replaced, if deemed necessary by the medical monitor to ensure that data are collected from a sufficient number of subjects. The medical monitor should be notified within 48 hours if a subject permanently discontinues study drug or withdraws consent to all follow-up. A determination whether to replace the subject will be made by the medical monitor.

Subject retention for dosing and for study procedures, even if dosing has been discontinued, is key to the success of this study. Sites must have a subject retention plan in place. The following approaches should be included to minimize loss of data: asking a subject for the name and contact number of a family member or friend who can be contacted to reach the subject (signed consent should be obtained); use of email contact (with care to avoid revealing confidential medical information over nonsecure email); and coverage of the cost of transportation to clinic, if needed.

For any missing visit/contact or missing data, the reason for the missing visit/contact and/or data must be recorded in the electronic data capture (EDC) system.

#### **4.1.8 Withdrawal of Informed Consent for Data and Biological Samples**

AstraZeneca ensures that biological samples are returned to the source or destroyed at the end of a specified period as described in the informed consent.

If a subject withdraws consent to the use of donated biological samples, the samples will be disposed of/destroyed, and the action documented. If samples are already analyzed, AstraZeneca is not obliged to destroy the results of this research.

As collection of the biological samples is an integral part of the study, then the subject is withdrawn from further study participation.

The Principal Investigator:

- Ensures subjects' withdrawal of informed consent to the use of donated samples is notified immediately to AstraZeneca. AstraZeneca will ensure the organization(s) holding the samples is/are informed about the withdrawn consent immediately and that samples

are disposed of/destroyed, the action documented and the signed document returned to the study site.

- Ensures that biological samples from that subject, if stored at the study site, are immediately identified, disposed of/destroyed, and the action documented and AstraZeneca are informed about the sample disposal.

## 4.2 Schedule of Study Procedures

Whenever vital signs, 12-lead ECGs, and blood draws are scheduled for the same nominal time, the blood draws should occur last. The timing of the first 2 assessments should be such that it allows the blood draw (eg, PK blood sample) to occur at the proper nominal time. Randomization should only proceed if all required assessments have been performed and all inclusion/exclusion criteria as well as other protocol restrictions have been evaluated; see Section 4.1.2, Section 4.1.3, and Section 4.7.

Dosing of subjects should only be carried out if all required assessments have been performed and evaluated. Dosing is not allowed to proceed until the investigator has determined that the results are within acceptable range according to the defined stopping criteria; see Section 4.1.6. Laboratory assessment results should also be reviewed at every visit to ensure that stopping criteria have not been met.

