### **1.7.2 Dapagliflozin**

The safety profile of dapagliflozin has been evaluated in clinical development programs for T2DM, T1DM, heart failure and CKD. This includes more than 15,000 subjects treated with

dapagliflozin for T2DM, more than 1,000 subjects treated with dapagliflozin for T1DM, more than 1,400 subjects treated with dapagliflozin for DKD, and more than 2,000 subjects treated with dapagliflozin for heart failure. Overall, treatment with dapagliflozin 5 mg was similar to treatment with dapagliflozin 10 mg in both T1DM and T2DM. The safety profile of dapagliflozin was overall consistent across the studied indications.

The most commonly reported AEs associated with the use of dapagliflozin include genital infections, urinary tract infections, back pain, and polyuria. In addition, rash has been identified as an AE of unknown frequency in marketed use of dapagliflozin.

In the cardiovascular outcomes study, dapagliflozin on the Incidence of Cardiovascular Events (DECLARE), 8,574 patients received dapagliflozin 10 mg and 8,569 patients received placebo for a median exposure time of 48 months. Events of diabetic ketoacidosis (DKA) were reported in 27 patients in the dapagliflozin 10 mg group and 12 patients in the placebo group. The events occurred evenly distributed over the study period. Of the 27 patients with DKA events in the dapagliflozin group, 22 had concomitant insulin treatment at the time of the event.

The DAPA-CKD renal outcome study has shown 10 mg dapagliflozin to be efficacious and well tolerated in a wide range of patients with CKD (2152 patients treated with dapagliflozin; median follow-up = 2.4 years) (Heerspink et al, 2020a). In patients with an estimated glomerular filtration rate (eGFR) 25 to 75 mL/min/1.73m^2 dapagliflozin was shown to significantly reduce the combined risk of: 1) sustained decline in eGFR of at least 50%; 2) end-stage kidney disease; 3) or death from renal or cardiovascular causes (Heerspink et al, 2020a).

Taken together, SGLT2i have been shown to consistently reduce the risk of clinically important, patient-level cardiovascular outcomes and emerging data suggest that the combination of ACEi or ARB and SGLT2i should be routinely offered to patients with T2DM who have, or are at high risk of, progressive kidney disease (de Boer et al, 2020).

More detailed information about the known and expected benefits and potential risks of dapagliflozin may be found in the respective current IB (Edition 17).

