**Table 2 Secondary Objectives and Associated Endpoints**

Type	Objective	Endpoint
		
 
• BNP
 
• Laboratory assessments (hematology, clinical chemistry, and urinalysis)
 
• For subjects testing positive for COVID-19 during the intervention and follow-up periods, the number and proportion of subjects with AEs/SAEs, as well as the number and proportion of subjects with COVID-19 AEs/SAEs, and the proportion of asymptomatic subjects.
 

PK, Immunogenicity	To describe the PK and immunogenicity of MEDI3506 in subjects with DKD	MEDI3506 serum concentrations and ADA incidence occurring throughout the study
Efficacy	To evaluate the effect of MEDI3506 in combination with ACEi or ARB with and without dapagliflozin on albuminuria in subjects with DKD	
 
• Proportion of subjects with > 30% reduction in UACR at Day 169 (Week 24)
 
• Proportion of subjects with > 40% reduction in UACR at Day 169 (Week 24)
 
• Proportion of subjects with > 50% reduction in UACR at Day 169 (Week 24)
 
• Change from baseline to Day 85 (Week 12) in UACR
 
• Change from Day 85 (Week 12) to Day 169 (Week 24) in UACR
 

ACEi = angiotensin converting enzyme inhibitors; ADA = anti-drug antibody; AE(s) = adverse event(s); ARB = angiotensin receptor blockers; BNP = B-type natriuretic peptide; ECG = electrocardiogram; EOS = end of study; DBP = diastolic blood pressure; DKD = Diabetic Kidney Disease; LVEF = left ventricular ejection fraction; PK = pharmacokinetic; SAE(s) = serious adverse event(s); SBP = systolic blood pressure; TEAE(s) = treatment emergent adverse event(s); TESAE(s) = treatment emergent serious adverse event(s); UACR = urine albumin to creatinine ratio

CCI

CCI

CCI

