**Table 6 Schedule of Treatment Period Study Procedures**

Study Period	Treatment Period							
Visit Number	V3	V4	V5	V6	V7	V8	V9	Early D/c Visit
Procedure / Study Day	Day 1	Day 29 (± 5 days)	Day 57 (± 5 days)	Day 85 (± 5 days)	Day 113 (± 5 days)	Day 141 (± 5 days)	Day 169 (± 5 days)	
Verify eligibility criteria	X							
Randomization	X							
Safety assessments:								
Physical examination (abbreviated) with weight a	X	X	X	X	X	X	X	X
Vital signs b	X	X	X	X	X	X	X	X
Transthoracic echocardiogram							X c	X
Assessment of AEs/SAEs	X	X	X	X	X	X	X	X
Concomitant medications	X	X	X	X	X	X	X	X
Blood collection for:								
Serum chemistry	X	X		X		X	X	X
CCI [REDACTED]	X	X		X			X	X
CCI [REDACTED]							X	X

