**Table 6 Schedule of Treatment Period Study Procedures**

Study Period	Treatment Period								
	Visit Number	V3	V4	V5	V6	V7	V8	V9	Early D/c Visit
Procedure / Study Day	Day 1	Day 29 (± 5 days)	Day 57 (± 5 days)	Day 85 (± 5 days)	Day 113 (± 5 days)	Day 141 (± 5 days)	Day 169 (± 5 days)		
Complete blood count with differential, prothrombin time, and PTT	X				X			X	X
PK (MEDI3506) d		X			X			X	X
PK (dapagliflozin) e						X	X		
ADA (MEDI3506) f	X	X			X			X	X
CCI									
CCI									
Blood for future use f,g	X	X					X		X
Genetic research sample g,h	X								
Urine collection for:									
Urinalysis f	X								
Pregnancy test (females of childbearing potential) f	X	X	X	X	X	X	X	X	X
UACR i	X	X	X	X	X	X	X	X	X
CCI									
Urine for future use f,g	X	X			X		X		X
Procedure:									
Site to remind patients to collect first morning void midstream urine samples 3 days before the next visit		X	X	X	X	X	X	X	X
IP administration (MEDI3506/placebo) j	X	X	X	X	X	X			
IP administration (dapagliflozin) k				Day 85 to Day 168 QD					

ADA = anti-drug antibody(ies); AE(s) = adverse event(s); CCI  
D/c = discontinuation; CCI  
CCI ; IP = investigational product; PK = pharmacokinetics; PTT = partial thromboplastin time; QD = once daily; SAE(s) = serious adverse event(s); CCI ; UACR = urine albumin:creatinine ratio V= Visit.

NOTE: Investigator should ensure that all subjects are contacted by phone 1 day prior to every visit for assessing COVID-19 symptoms and signs and are asked to follow up suspected reports according to local guidelines. Any subject with symptoms consistent with COVID-19 should be tested on an ad hoc basis.

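### Urinalysis is a named safety endpoint component but is not scheduled between Day 1 and Day 230, and the pre-dose laboratory check relies on a range that Section 4.1.6 does not give

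*Protocol*

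**What the plan says.** **Endpoint.** Protocol Section 2.2, Table 2, sets a secondary objective of safety and tolerability of MEDI3506 with and without dapagliflozin. Its endpoints include "Laboratory assessments (hematology, clinical chemistry, and urinalysis".

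**Urinalysis schedule.** Table 5 marks urinalysis at Visit 1 (screening). In Table 6 the row reads "Urinalysis f X": one mark, in the first column (Day 1). Table 7 marks it at Visit 10 (Day 230). The Early Discontinuation column of Table 6 has no mark.

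**Chemistry and hematology schedule.** The Table 6 row "Serum chemistry X X X X X X" has six marks over eight columns: Days 1, 29, 85, 141, 169 and Early Discontinuation. Days 57 and 113 are blank. The row "Complete blood count with differential, prothrombin time, and PTT" is marked at Days 1, 85, 169 and Early Discontinuation.

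**Pre-dose rule.** Section 4.2 states: "Dosing is not allowed to proceed until the investigator has determined that the results are within acceptable range according to the defined stopping criteria", and refers to Section 4.1.6. It then adds: "Laboratory assessment results should also be reviewed at every visit to ensure that stopping criteria have not been met". Section 4.1.6 lists reasons for ending treatment and points to Appendix C for liver biochemistry. It states no other laboratory range.

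**Context.** Section 1.7.2 says: "The most commonly reported AEs associated with the use of dapagliflozin include genital infections, urinary tract infections, back pain, and polyuria". Section 4.3.3 lists ketones, leukocytes, blood, glucose and protein in the urinalysis panel.

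**The concern.** There are two separate mismatches.

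The first lies between the endpoint and the schedule. A safety endpoint component needs at least one sample taken while the subject is exposed. Urinalysis has a baseline and a follow-up value with nothing between them. No later analysis plan can recover samples that were never scheduled. The component is then reported under an objective that it cannot address, for MEDI3506 alone (Day 1 to Day 85) or with dapagliflozin (Day 85 to Day 168).

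The second lies within the dosing rule. Section 4.2 makes each dose conditional on results being in an acceptable range under defined criteria. The section it cites does not define that range, and at two dosing visits no chemistry is drawn. Sites cannot tell from the text which results, how recent and against what limits, make up the check, so they may apply it differently.

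**Working it through.** The plan states no figure on this point, so there is none to reproduce. The check sets the schedules side by side and counts days.

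**Inputs.** Visit days, tests and MEDI3506/placebo doses come from Tables 6 and 7. Dapagliflozin from Day 85 to Day 168 comes from Section 3.1.2.

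| Visit day | MEDI3506/placebo dose | Dapagliflozin | Chemistry | Hematology | Urinalysis |
|---|---|---|---|---|---|
| 1 | yes | no | X | X | X |
| 29 | yes | no | X | – | – |
| 57 | yes | no | – | – | – |
| 85 | yes | starts | X | X | – |
| 113 | yes | yes | – | – | – |
| 141 | yes (last) | yes | X | – | – |
| 169 | no | ended Day 168 | X | X | – |
| Early Discontinuation | no | – | X | X | – |
| 230 | no | no | X | X | X |

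**Urinalysis**
- Scheduled samples after Day 1 and on treatment: 0.
- Gap between scheduled samples: 230 − 1 = 229 days.
- Day 230 relative to the last scheduled MEDI3506 dose: 230 − 141 = 89 days. With ±5-day windows on both visits, the range is 225 − 146 = 79 to 235 − 136 = 99 days.
- Day 230 relative to the last dapagliflozin tablet: 230 − 168 = 62 days. With ±5 days on Day 230, the range is 57 to 67 days.
- Early discontinuers: no urinalysis at the Early Discontinuation Visit. Section 4.1.6 places Visit 10 at 60 ± 5 days after the last visit performed, so their value is also off treatment.

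**Chemistry**
- Gaps between scheduled samples: 29 − 1 = 28; 85 − 29 = 56; 141 − 85 = 56; 169 − 141 = 28 days.
- Doses with chemistry at the same visit: 4 of 6. The exceptions are Day 57 and Day 113.
- Dapagliflozin period: 168 − 85 + 1 = 84 days. The first scheduled chemistry after its start comes at 56 days (136 − 90 = 46 to 146 − 80 = 66 with windows), and 56/84 = 67% of the period.
- Time points that reflect dapagliflozin: chemistry at Day 141 and Day 169 (one day after the last tablet), hematology at Day 169.

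**Pre-dose rule.** Section 4.2 refers to Section 4.1.6, which refers to Appendix C. Appendix C gives liver thresholds for identifying and reporting potential Hy's Law cases and says that it is not a full guide to managing elevated liver tests. The chain supplies no acceptable range for the other scheduled laboratory tests.

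**The case against.** **Review is not the same as drawing a sample.** Section 4.2 asks for results to be reviewed at every visit. At Day 113 the Day 85 results can be reviewed. This stands: the blank chemistry cells do not by themselves contradict the rule. What remains is that the text does not say which results count, and the range it relies on is absent from Section 4.1.6.

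**Other safeguards exist.** Extra blood may be drawn for an adverse event or an abnormal result (Section 4.3.8), further assessments are at the investigator's discretion (Section 4.3.2), and suspected ketoacidosis has its own instruction (Sections 4.1.6 and 4.7.3). Urinary infections are recorded as adverse events. This also stands, so the gap does not leave those events undetected. Event-driven tests, however, do not provide a by-arm urinalysis endpoint.

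**Sparse sampling was a choice.** The stated rationale of Amendment 4 was to reduce participant burden. That explains a thin schedule, but not an endpoint component with no exposed sample.

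**Stronger readings that the documents do not support**
- A reader might infer that the whole laboratory endpoint fails on the combination. Chemistry at Days 141 and 169 and hematology at Day 169 can be summarized by arm, as Section 4.8.4.2 plans.
- A reader might infer that the chemistry gap is peculiar to the combination. The same 56 days separate Day 29 from Day 85.
- A reader might infer that no chemistry drawn on the combination informs a MEDI3506 dose, because Day 141 is the last dosing visit. That depends on central-laboratory turnaround, which the protocol does not state.
- A reader might infer a planned urinalysis shift table that shows only washout. Section 4.8.4.2 names chemistry and hematology and does not expressly promise one for urinalysis.
- A reader might take all subjects to be newly exposed at Day 85. Some switch from an existing SGLT2 inhibitor, some who passed Week 12 before Amendment 2 receive no dapagliflozin, and those who stop MEDI3506 before Day 85 do not proceed to it.

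**Conclusion.** The point holds in two parts. First, the urinalysis component of the secondary laboratory safety endpoint has no scheduled on-treatment sample after Day 1. Its only post-baseline value comes 89 days after the last scheduled MEDI3506 dose and 62 days after the last dapagliflozin tablet, so it cannot inform the objective either with or without dapagliflozin. Second, the dosing condition in Section 4.2 relies on a laboratory range that Section 4.1.6 does not supply, and Table 6 schedules no chemistry at 2 of 6 dosing visits. These passages need reconciling. Neither part affects the primary UACR analysis, and the chemistry and hematology components remain usable, if thin.

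Three assumptions apply. The Day 1 urinalysis is taken as baseline. The hematology columns in the second part of Table 6 are shifted in the extracted text and were aligned using the MEDI3506 PK row; the single urinalysis mark is in the first column either way. The text of footnote f to the urinalysis row does not appear in the public copy. Since ADA, pregnancy testing and future-use samples share that footnote, it is assumed not to add urinalysis visits. Some laboratory rows are redacted and were not judged.

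**What to change.** **Reconcile Table 2 with Tables 6 and 7, in one of two ways.**
- Mark urinalysis at on-treatment visits before and during the dapagliflozin period and at Early Discontinuation. Urine is already returned for UACR at every treatment visit and could be used where suitable. Two of the three samples are ideally from the preceding days and refrigerated, so suitability for microscopy needs confirming with the laboratory. The panel includes protein, and Table 1 blinds UACR results from Day 1 through the end-of-study visit, so the protein result should be withheld from sites.
- Or remove urinalysis from the on-treatment safety endpoint and describe it as a baseline and follow-up assessment only.

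**Reconcile Section 4.2 with Table 6 and Section 4.1.6.** State which results are reviewed before each dose, including at Days 57 and 113, and where the acceptable range is defined. The content of that rule is for the sponsor to settle.

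**Leave the Day 141 chemistry where it is.** Moving it to Day 113 would only shift the gap (169 − 113 = 56 days) and leave the last MEDI3506 dosing visit without chemistry.

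**Cost.** A table or wording amendment. If urinalysis is added, there is also a small laboratory fee, a change to the laboratory set-up and masking of the protein result.

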### 4.2.1 Enrollment/Screening Period

Table 5 shows all procedures to be conducted at the screening visit.

**Table 5 Schedule of Screening Procedures**

Study Period	Screening		
	Visit 1	Phone Call 1 a	Visit 2
Procedure / Study Day	Day -37 to Day -3		
Informed consent (main study)	X		
Informed consent (future use blood and urine b )	X		
Informed consent (genetic b )	X		
Verify eligibility criteria	X	X	
Safety assessments:			
Full medical history review	X		
Assessment of AEs/SAEs		X	X
Physical examination (full)	X		
Weight, height, and BMI calculation	X		
Vital signs	X		
ECG	X		

**Table 5 Schedule of Screening Procedures**

Study Period	Screening		
	Visit 1	Phone Call 1 a	Visit 2
Procedure / Study Day	Day -37 to Day -3		
Transthoracic echocardiogram			X c
Concomitant medications	X	X	X
Blood collection for:			
Serum chemistry	X		
CCI	X		
CCI	X		
Serum beta-hCG, FSH (for women) d	X		
Complete blood count with differential	X		
eGFR calculation e	X		
Hepatitis B, C; HIV-1, HIV-2	X		
Urine collection for:			
Urinalysis	X		
Drug and alcohol screen f	X		
Spot urine for UACR	X		
Procedure:			
Dispense supply of containers for urine samples	X		
Reminder to collect first morning void midstream urine samples 3 days before the next visit		X	
Subjects return first morning void midstream urine collection samples for UACR analysis g			X

AE(s) = adverse event(s); ALT = alanine aminotransferase; AST = aspartate aminotransferase; BMI = body mass index; CCI; ECG = 12-lead electrocardiogram; eGFR = estimated glomerular filtration rate; FSH = follicle-stimulating hormone; CCI hCG = human chorionic gonadotropin; HIV = human immunodeficiency virus; PTT = partial thromboplastin time; SAE(s) = serious adverse event(s); UACR = urine albumin:creatinine ratio.

NOTE: Where the values for clinical laboratory tests (Section 4.3.3) are outside the usual range for a subject during screening, based on their medical history, retesting may be undertaken on one occasion without requiring a re-screen.

NOTE: Investigator should ensure that all subjects are contacted by phone 1 day prior to every visit for assessing COVID-19 symptoms and signs and are asked to follow up suspected reports according to local guidelines.

a Phone Call 1 will occur after results from the initial screening visit are available and the subject is confirmed otherwise eligible in order to remind subjects to collect the first morning void and schedule Visit 2.

b Optional informed consent is required for agreement to the future use of blood and urine samples and genetic testing, if appropriate.

**Table 5 Schedule of Screening Procedures**

Study Period	Screening		
Visit Number	Visit 1	Phone Call 1 a	Visit 2
Procedure / Study Day	Day -37 to Day -3		

- c If otherwise eligible at Screening Visit 1, a Screening Visit 2 will be scheduled to conduct the transthoracic echocardiogram, which may be performed independently of other Visit 2 procedures during the screening period.
- d Testing for menopause will only be performed if menopausal status cannot be established from full medical history review.
- e For subjects with amputation, eGFR will be adjusted based on estimated body weight loss.
- f Alcohol screen breathalyzer to be performed in line with local practices. Drug screen to be performed in line with local practices and investigator discretion.
- g Subjects collect 3 consecutive first morning void midstream urine samples (ideally day of visit and preceding 2 days [refrigerated overnight]) which are returned on the day of visit. This collection may be repeated once during the course of screening. Eligibility will be determined based on the results.

